**Table 6-1: Study treatment for Part A**

Treatment name	UCB0599 180mg/day capsules	UCB0599 180mg/day tablets	UCB0599 180mg/day encapsulated tablets	Co-administration of PPI
Intervention name	UCB0599	UCB0599	UCB0599	Esomeprazole
Type	Drug	Drug	Drug	Drug
Dose formulation	Granules in oral capsules (reference formulation)	Oral film-coated tablets with CCI [REDACTED]	Oral encapsulated tablets with CCI [REDACTED]	Oral capsules
Unit dose strength(s)	90mg	180mg	180mg	40mg capsules (Nexium® delayed-release capsule)
Dosage level(s)	180mg/day SD (2x90mg capsules)	180mg/day SD (1 tablet)	180mg/day SD (1 encapsulated tablet)	40mg QD (1 capsule)
Route of administration	Oral	Oral	Oral	Oral
Use	Experimental	Experimental	Experimental	Experimental
IMP and NIMP/AxMP	IMP	IMP	IMP	NIMP
Sourcing	Provided centrally by the Sponsor	Provided centrally by the Sponsor	Provided centrally by the Sponsor	Sourced locally by the clinical site
Packaging and labeling	The study medication is manufactured, packaged, and labeled according to GMP guidelines and in accordance with all applicable laws or regulations. Each study medication bottle will be labeled according to individual country requirements. Details of the packaging and labeling will	The study medication is manufactured, packaged, and labeled according to GMP guidelines and in accordance with all applicable laws or regulations. Each study medication bottle will be labeled according to individual country requirements. Details of the	The study medication is manufactured, packaged, and labeled according to GMP guidelines and in accordance with all applicable laws or regulations. Each study medication bottle will be labeled according to individual country requirements. Details of the	NA

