### **8.3.1        Time period and frequency for collecting AE and SAE information**

All AEs and SAEs will be collected from the signing of the ICF until the SFU Visit at the time points specified in the Schedule of Activities (Section 1.3 for Part A [[Table 1-3](#)] and Part B [[Table 1-4](#)]).

In order to ensure complete safety data collection, all AEs occurring during the study (ie, after the signing of the ICF), including any pretreatment and posttreatment periods required by the protocol, must be reported in the eCRF even if no study medication was taken but specific study procedures were conducted. This includes all AEs not present prior to the initial visit and all AEs that recurred or worsened after the initial visit.

All SAEs will be recorded and reported to the sponsor or designee within 24 hours, as indicated in Appendix 3 (Section 10.3). The Investigator will submit any updated SAE data to the Sponsor within 24 hours of it being available.

The Investigator is specifically requested to collect and report to UCB (or its representative) any SAEs (even if the Investigator is certain that they are in no way associated with the study medication), up to 30 days from the end of the study for each participant, and to also inform participants of the need to inform the Investigator of any SAE within this period. Serious AEs that the Investigator thinks may be associated with the study medication must be reported to UCB regardless of the time between the event and the end of the study.

The method of recording, evaluating, and assessing causality of AE and SAE and the procedures for completing and transmitting SAE reports are provided in Appendix 3 (Section 10.3).

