5.1.1 General study level definitions

5.1.1.1 Analysis Time Points

5.1.1.1.1 Relative day

Relative day will be derived with the date of treatment in each Period (treatment and washout) as reference for that specific Period.

- Relative Day 1 is the date of treatment.

- For days prior to first treatment:

Relative day = Current date – Date of first treatment.

- For days after the day of treatment in Period:

Relative day = Current date - Date of treatment within the same Dosing Period +1.

- For days after the day of last treatment:

Relative day = Current date - Date of last treatment +1.

There is no Relative day 0. Relative day will not be calculated for partial dates. Relative day for partial days will be displayed as ‘--’ to distinguish it from missing values which are displayed as blanks.

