5.5.2 Adverse Events

An Adverse Event is any untoward medical occurrence in a participant or clinical study participant, temporally associated with the use of study medication, whether considered related to the study medication.

Adverse events with start date/time prior to first treatment are defined as pre-treatment. These events will not be included in any tabulated summaries, but will be listed.

Treatment emergent AEs (TEAE) are all AEs starting on or after the date/time of first treatment and up to including 4 days after last treatment, or any unresolved event already present before administration of treatment that worsens in intensity following exposure to the treatment.

AEs with a start date after 4 days of last treatment are defined as post-treatment. These events will not be included in any tabulated summaries, but will be listed.

In case of missing or partially missing AE dates, the following rules will apply. Start and stop dates of AEs will be displayed as reported in the participant data listings (ie, no imputed values will be displayed in data listings).

The following rules will be applied for partial start dates and time:

- If only the month and year are specified and the month and year of the first treatment is not the same as the month and year of the start date, then use the 1st of the month, or the date of Screening if this is later (if the imputation results in an end date that is earlier than the start date, then use the 1st of the month). If time is missing, it will be imputed as 00:00 h
- If only the month and year are specified and the month and year of the first treatment is the same as the month and year of the start date, then use the date of the first treatment. If the imputed start date that is after the specified end date, then use the 1st of the month, or the date of Screening if this is later (if the imputation results in an end date that is earlier than the start date, then use the 1st of the month). If the imputed date is the date of treatment then time will be imputed as the start time of the treatment (ie, event will be regarded as treatment emergent)
- If only the year is specified, and the year of the first treatment is not the same as the year of the start date, then January 01 will be used. If time is missing, it will be imputed as 00:00 h

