Adverse events will be assigned to Treatment Periods, based on the onset date/time of the AE. Assignment to Treatment Periods will be done after missing dates have been imputed as described above. AE will be assigned to a treatment based on the treatment received in the Treatment Periods as given in [Table 5-8](#).

Table 5-8: AE Treatment Period Assignment

Study Part	Period	Start	End
Part A	Treatment Period 1	Start date is on or after administration of treatment in Treatment Period 1	Prior to administration of treatment in Treatment Period 2
	Treatment Period 2	Start date is on or after administration of treatment in Treatment Period 2	Prior to administration of treatment in Treatment Period 3
	Treatment Period 3	Start date is on or after administration of treatment in Treatment Period 3	Prior to administration of treatment in Treatment Period 4
	Treatment Period 4	Start date is on or after administration of treatment in Treatment Period 4	Prior to administration of treatment in Treatment Period 5
	Treatment Period 5	Start date is on or after administration of treatment in Treatment Period 5	Prior to administration of treatment in Treatment Period 6
	Treatment Period 6	Start date is on or after administration of treatment in Treatment Period 6	
Part B	Treatment Period 1	Start date is on or after administration of treatment in Treatment Period 1	Prior to administration of treatment in Treatment Period 2
	Treatment Period 2	Start date is on or after administration of treatment in Treatment Period 2	

The following summaries will be provided for Part A by formulation and for Part B by dose level and group:

- Incidence of TEAEs – Overview
- Incidence of TEAEs
- Incidence of Serious AEs
- Incidence of TEAEs leading to discontinuation
- Incidence of TEAEs by maximum intensity
- Incidence of TEAEs by relationship to study medication

AEs will be presented as “number of participant (percentage of participant) [number of events]”. In this style of output, “[number of events]” will include all cases of an AE including repeat occurrences in individual participant, while “number of participant” will count each participant only once.

AEs will be presented by system organ class (SOC), high level term (HLT) and preferred term (PT) in a frequency table, giving the number of events, the number of participants, and the percentage of participants who experienced the event. Participants with multiple AEs are only counted once within each PT, each HLT and within each SOC.

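### SAP 5.5.2 keeps new-onset AEs, SAEs included, out of every summary table once 4 days have passed since last treatment, although the protocol collects them and plans an SAE summary without that limit

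*SAP*

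**What the plan says.** SAP 5.5.2 counts an AE as treatment-emergent if it starts between first treatment and 4 days after last treatment, or if an event already present worsens after exposure. For later onsets it says: "AEs with a start date after 4 days of last treatment are defined as post-treatment. These events will not be included in any tabulated summaries". They are listed. One of the planned tables is "Incidence of Serious AEs", a title without a treatment-emergent limit.

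Table 5-8 attributes events to periods: "AE will be assigned to a treatment based on the treatment received in the Treatment Periods". For the last period of Part A it gives a start, "Start date is on or after administration of treatment in Treatment Period 6", and no end. Part B Period 2 is treated the same way.

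Protocol 8.3.1 sets the collection period: "All AEs and SAEs will be collected from the signing of the ICF until the SFU Visit". It adds that events in "any pretreatment and posttreatment periods required by the protocol, must be reported in the eCRF". The same section asks for SAEs for 30 days beyond each participant's end of study. Protocol 9.5.1 sorts AEs into two classes, before treatment and treatment-emergent, and plans a summary of SAEs by treatment and ethnic group. SAP Appendix 4 (changes to protocol-planned analyses) is marked not applicable.

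**The concern.** The SAP adds a third AE class that the protocol does not have and removes it from all tables. The SFU visit includes laboratory tests, ECG, vital signs and a physical examination, and Protocol 8.2 has clinically relevant findings recorded as AEs. If every permitted SFU date lies after the cut-off, a new event first arising in follow-up can never enter an incidence table. For a serious event, it would be collected, sent to the sponsor within 24 hours and listed, yet absent from the table headed as the incidence of serious AEs. Safety is a primary objective in Part B and a secondary one in Part A, so a reader of the report tables could take a zero to cover the whole observation period when it does not.

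**Working it through.** **Inputs.** Last UCB0599 or placebo dose: Day 29 in Part A, Day 6 in Part B (Protocol Tables 1-1 and 1-2). SFU visit: Day 37 ± 2 and Day 13 ± 2 (Protocol Tables 1-3 and 1-4). Window: 4 days after last treatment (SAP 5.5.2).

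**Which date is last treatment?** SAP 5.1.1.1.1 gives "Relative day = Current date - Date of last treatment +1". SAP Table 5-1 starts Part A follow-up on Day 34 at Relative Day +6.
- From Day 29 (last UCB0599 dose): 34 − 29 + 1 = 6, which matches.
- From Day 33 (last esomeprazole dose): 34 − 33 + 1 = 2, which does not.
- Washout 6, Days 30 to 33, gives +2 to +5 from Day 29, as printed.
- Day 39 gives +11 where the table prints +10, a slip that does not change the inference.

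**Days listed only, up to the SFU visit** (SFU day minus cut-off):

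| | Cut-off | Early SFU | Nominal SFU | Late SFU |
|---|---|---|---|---|
| Part B | 6 + 4 = Day 10 | 11 − 10 = 1 | 13 − 10 = 3 | 15 − 10 = 5 |
| Part A | 29 + 4 = Day 33 | 35 − 33 = 2 | 37 − 33 = 4 | 39 − 33 = 6 |

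Every permitted SFU date is after the cut-off in both parts.

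As a share of the days from last dose to SFU:
- Part B: 3/7 = 43% (1/5 = 20% to 5/9 = 56%).
- Part A: 4/8 = 50% (2/6 = 33% to 6/10 = 60%).

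In participant-days at the nominal visit, if all complete:
- Part B: 30 × 3 = 90, of which 24 × 3 = 72 on UCB0599 and 6 × 3 = 18 on placebo.
- Part A: 36 × 4 = 144 to 42 × 4 = 168.

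**SAEs.** Taking each participant's end of study as the nominal SFU visit, collection runs to Day 13 + 30 = 43 in Part B and Day 37 + 30 = 67 in Part A. The listed-only span is then 43 − 10 = 33 days and 67 − 33 = 34 days.

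**Evenness within Part A.** Period 3 is dosed on Day 11 and Period 4 on Day 19. An onset on Days 16 to 18 is 5 to 7 days after the Day 11 dose. It falls between first treatment and the end of the window, so it is treatment-emergent, and Table 5-8 assigns it to Period 3. The same 5 to 7 day lag after Day 29 (Days 34 to 36) is post-treatment and untabulated.

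**Balance.** By design, each Part B active dose is the last dose for 4 participants per ethnic group, so each loses 4 × 3 = 12 participant-days. In Part A each formulation is last in two of the six sequences.

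**The case against.** The protocol sets no treatment-emergent window, so 4 days is the SAP's to choose, and it equals the washout length and the 96-hour sampling span. The endpoints are the incidence of TEAEs and treatment-emergent SAEs, so an event outside the window is outside the endpoint by definition. The registry table is titled for serious TEAEs and correctly holds only those. Late events appear in a listing that flags SAEs and events of special interest; the registry overview has an all-deaths line; study discontinuation due to AEs is tabulated without the limit (SAP 5.2). With 15 participants per ethnic group, a listing shows every case. All of this stands, and it limits the point to reporting. It does not answer Protocol 9.5.1, whose SAE summary carries no treatment-emergent limit, or Appendix 4, which declares no change.

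Two stronger readings are tempting, and the documents do not support them.
- A reader might infer that 5.5.2 and Table 5-8 contradict each other, because the last period has no end. They do different jobs: 5.5.2 decides what is tabulated, and Table 5-8 attributes events to a treatment. The listing of all AEs by formulation or dose level needs that attribution for late events too.
- A reader might infer that last treatment is undefined in Part A, because "Table 6-1: Study treatment for Part A" has an esomeprazole column and esomeprazole runs to Day 33. No sentence defines the term, but SAP Table 5-1 fits only the Day 29 dose.

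**Conclusion.** The point holds as a reporting gap that should be closed. A stated SAP rule removes new-onset post-treatment events, SAEs included, from all tables, departs from the SAE summary planned in Protocol 9.5.1 without being recorded as a change, and treats equal lags differently within Part A. At the nominal visit it affects 3 days of follow-up in Part B and 4 in Part A, plus about 33 and 34 days of SAE collection counted from the cut-off.

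The figures assume that last treatment means the last UCB0599 or placebo dose, and the SAE spans assume that the study ends for each participant at the nominal SFU visit. They are calendar days, not events: the documents give no late-event rate, so the number of events concerned cannot be estimated and may be zero. The rule applies to new onsets; the worsening limb of the TEAE definition has no end date. A reader might infer lost safety data, a breach of a protocol window, or bias between doses. None follows: the events are listed, the protocol has no such window, and the planned doses and formulations are affected equally.

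**What to change.** Keep the 4-day TEAE window; TEAE counts and the equal Part B windows (Days 1 to 5 and Days 6 to 10) then stay as they are.

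1. Amend the exclusion sentence in SAP 5.5.2.
2. Add a separate post-treatment row or column to the AE incidence tables, covering onset after the window through the SFU or early termination visit.
3. Add the same to the table of serious AEs, covering all SAEs collected, including those after SFU. Attribute both to the last treatment received.
4. Record the window and its rationale in SAP Appendix 4.

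Two minor clarifications: label the later part of the last period in Table 5-8 as post-treatment, without cutting it off, since the listing needs the attribution; and state that last treatment means the last UCB0599 or placebo dose, as Table 5-1 implies.

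The cost is SAP wording and one extra row or column. No new data are needed. SAP version 1 (05 Sep 2023) predates Protocol Amendment 1 (26 Oct 2023), so the edits can go into an alignment update. The one drawback is that a few late events, perhaps unrelated to treatment, will be shown.

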## Overall design

UP0073 is a randomized, 2-part single-dose crossover Phase 1 study. A study overview of UP0073 is provided in [Figure 1-1](#).

The primary objective of Part A is to estimate the relative bioavailability of 2 new UCB0599 formulations (180mg film-coated tablet containing **CCI** with or without encapsulation) versus the current clinical formulation (2x90mg granules in capsule) under both normal and elevated gastric pH conditions. This portion of the study is an open-label, randomized, 2 in-series crossover substudies, each with a fixed sequence complete block design of 3 treatment periods in healthy male and female participants. The secondary objective is to evaluate the safety and tolerability of a single dose UCB0599 alone under normal and elevated gastric pH. Other objectives are to further evaluate the PK of UCB0599 and its metabolites (**CCI**) after a single-dose UCB0599 alone and co-administrated with esomeprazole. See Section 3 for more details on the objectives and endpoints of the study.

Part B of this study is an ethnobridging study evaluating the safety, tolerability, and PK of a single oral dose of UCB0599 at 3 dose levels (90mg, 180mg, and 360mg) under normal gastric pH conditions in healthy participants of Japanese and Chinese origins. Each group of ethnic origin (N=15 total for each) will be randomized to a 4-treatment, 6-sequence, 2-period crossover study using UCB0599:placebo in a 4:1 ratio, as shown below and in the Study Schema (see Section 1.2). Sequences 3 and 4 will only commence after Sequences 1 and 2 have been completed for all 5 participants; Sequences 5 and 6 will only commence after Sequences 3 and 4 have been completed for all 5 participants, allowing the Safety Monitoring Committee (SMC) review to be carried out before the start of Sequence 5.

- Sequence 1: placebo 90mg, followed by placebo 180mg (N=1)
- Sequence 2: UCB0599 90mg, followed by UCB0599 180mg (N=4)
- Sequence 3: placebo 180mg, followed by placebo 360mg (N=1)
- Sequence 4: UCB0599 180mg, followed by UCB0599 360mg (N=4)
- Sequence 5: placebo 360mg, followed by placebo 90mg (N=1)
- Sequence 6: UCB0599 360mg, followed by UCB0599 90mg (N=4)

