## 1.2 Schema

Figure 1-1: Overall study schematic

C=Chinese participants; J=Japanese participants; PK=pharmacokinetic(s); PPI=proton pump inhibitor; QD=once daily; SMC=Safety Monitoring Committee

Note: **A**: 180mg (90mg x 2 granules in capsule) current clinical formulation (reference formulation); **B**: 180mg non-encapsulated tablet containing **CCI** [REDACTED]; **C**: 180mg encapsulated tablet containing **CCI** [REDACTED].

Note: The PPI esomeprazole 40mg QD will be administrated on 20-consecutive days during substudy 2.

**Table 1-1: Part A design: Relative bioavailability of UCB0599 under normal or elevated gastric pH conditions in healthy participants (3-treatment, 6-period complete block design)**

Sequence (Duration)	Period 1 (D1)	WO (D2-5)	Period 2 (D6)	WO (D7-10)	Period 3 (D11)	WO a (D12-18)	Period 4 (D19)	WO (D20-23)	Period 5 (D24)	WO (D25-28)	Period 6 (D29)	WO (D30-33)
1 (ABC)	A		B		C	PPI start (D14)	A		B		C	
2 (ACB)	A		C		B	PPI start (D14)	A		C		B	
3 (BCA)	B		C		A	PPI start (D14)	B		C		A	
4 (BAC)	B		A		C	PPI start (D14)	B		A		C	
5 (CAB)	C		A		B	PPI start (D14)	C		A		B	
6 (CBA)	C		B		A	PPI start (D14)	C		B		A	

D=day; PPI=proton pump inhibitor; QD=once daily; WO=Washout Period

Note: A: 180mg (90mg x 2 granules in capsule) current clinical formulation (reference formulation); B: 180mg non-encapsulated tablet containing **CCI** **CCI**; C: 180mg encapsulated tablet containing **CCI**

Note: The washout of UCB0599 will take place after each period and last for 4 days.

Note : All 6 dosing days will be in a fasted state. In Treatment Period 1 through Period 3, study participants will fast overnight for at least 10 hours prior to study medication administration on Day 1, Day 6, and Day 11, and will continue to fast for at least 4 hours post-study medication administration. In Treatment Period 4 through Period 6, study participants will fast overnight for at least 9 hours prior to esomeprazole administration on Day 19, Day 24, and Day 29, and will continue to fast prior to study medication administration, which will be taken 1 hour following esomeprazole administration, and for at least 4 hours post-study medication administration. No fluid intake, apart from the fluid given at the time of study medication intake, is allowed from 2 hours before until 2 hours after dosing of study medication (Section 5.3.1).

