**Table 1-3: Part A Schedule of activities**

Procedure	Screening	Treatment Period 1—6 a													SFU b / ETV
		In-Clinic Period													
	D-28 to D-2	D-1	D1	D2 to D5	D6	D7 to D10	D11	D12 to D18 c	D19	D20 to D23	D24	D25 to D28	D29	D30 to D33	Day 37 (± 2 days)
Vital signs j	X	X	X		X		X		X		X		X		X
Randomization		X k													
Study medication administration k			X		X		X		X		X		X		
Esomeprazole administration c								X	X	X	X	X	X	X	
Adverse event review	X	X	X	X	X	X	X	X	X	X	X	X	X	X	X
Concomitant medication review	X	X	X	X	X	X	X	X	X	X	X	X	X	X	X
Blood sampling for PK 			X	X	X	X	X	X	X	X	X	X	X	X	
Genetic blood sampling			X m												
Meals		X n	X o	X n	X o	X n	X o	X n	X o	X n	X o	X n	X o	X n	
Confinement		X	X	X	X	X	X	X	X	X	X	X	X	X	X p

AKI=acute kidney injury; BMI=body mass index; BP=blood pressure; COVID-19=Coronavirus Disease 2019; D=Day; ECG=electrocardiogram;

ETV=Early Termination Visit; HBsAg=hepatitis B surface antigen; HCV=hepatitis C virus; HIV=human immunodeficiency virus; IRT=interactive response technology; PCR=polymerase chain reaction; PK=pharmacokinetic(s); QD=once daily; SARS-CoV-2=severe acute respiratory syndrome coronavirus 2; SFU=Safety Follow-Up

a Each study participant will attend 6 treatment periods and will be in the clinical center for every Treatment Period 1, 2, 3, 4, 5 and 6. In Treatment Period 4, an oral dose of 40mg esomeprazole will be administered QD for 20-consecutive days from Day 14 to Day 33. On Day 19, Day 24, and Day 29, a single oral dose of 180mg UCB0599 will be administered 1 hour after intake of esomeprazole. All 6 dosing days will be in a fasted state (Section 5.3.1). The washout of UCB0599 will take place after each period and last for 4 days.

b Study participants will have SFU procedures performed within 10 days after last dose. Participants who prematurely withdraw from the study will have the ETV as soon as possible after the time of withdrawal, and will have all SFU procedures performed.

c An oral dose of 40mg esomeprazole will be administered QD for 20-consecutive days from Day 14 to Day 33.

d The physical examination will only be performed on Day 14 and Day 33 during the treatment periods.

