Note: All 6 dosing days will be in a fasted state. In Treatment Period 1 through Period 3, study participants will fast overnight for at least 10 hours prior to study medication administration on Day 1, Day 6, and Day 11, and will continue to fast for at least 4 hours post-study medication administration. In Treatment Period 4 through Period 6, study participants will fast overnight for at least 9 hours prior to esomeprazole administration on Day 19, Day 24, and Day 29, and will continue to fast prior to study medication administration, which will be taken 1 hour following esomeprazole administration, and for at least 4 hours post-study medication administration. No fluid intake, apart from the fluid given at the time of study medication intake, is allowed from 2 hours before until 2 hours after dosing of study medication (Protocol Section 5.3.1).

* The PPI esomeprazole will be administrated at a dose of 40mg QD starting at the Washout Period and for 20-consecutive days (D14-D33).

Table 1-4: Part B design: The PK of UCB0599 in healthy Japanese and Chinese participants under normal gastric pH condition (4-treatment, 6-sequence, 2-period crossover design)

Sequence (Duration)	Period 1 (D1)	WO (D2-5)	Period 2 (D6)	WO (D7-10)
1	Placebo 90mg SD		Placebo 180mg SD	
2	UCB0599 90mg SD		UCB0599 180mg SD	
3	Placebo 180mg SD		Placebo 360mg SD	
4	UCB0599 180mg SD		UCB0599 360mg SD	
5	Placebo 360mg SD		Placebo 90mg SD	
6	UCB0599 360mg SD		UCB0599 90mg SD	

D=day; PK=pharmacokinetic(s); SD =single dose; WO=Washout Period.

Note: Of the 30 study participants enrolled in Part B, 15 participants of each ethnic origin will be randomized to the 4 treatments (placebo SD, UCB0599 90mg SD, UCB0599 180mg SD, and UCB0599 360mg SD) following a UCB0599:placebo 4:1 ratio. All participants will be dosed under fasting conditions. Study participants will fast overnight for at least 10 hours prior to study medication administration and will continue to fast for at least 4 hours post-study medication administration. No fluid intake, apart from the fluid given at the time of study medication intake, is allowed from 2 hours before until 2 hours after dosing of study medication (Protocol Section 5.3.1). The Washout Period will take place after each period and last for 4 days.

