5.2 Participant Dispositions

Participant screening and primary reason for screen failure will be summarized using the ASPS, separately for Part A and Part B. The summaries will include the following:

- Number of participants screened
- Number and proportion of participants rescreened
- Number and proportion of participants with screen failures (Not counting successfully rescreened participants)
- Number and proportion of screen failures by primary reason for screen failure (Based on the later screening visit)

By-participant listings of rescreened participants will be presented using the ASPS.

Participant disposition will be summarized using the ASPS, separately for Part A and Part B. Each summary will include the following:

- Date of first screening visit
- Date of last visit for last participant
- Number of participants screened
- Number of participants in each analysis set, by treatment sequence (according to randomized treatment).

Disposition of analysis sets will be tabulated using the ASPS, separately for Part A and Part B. Each table will present the total number of participants in the ASPS, as well as the number and percentage of participants in each analysis set by treatment sequence.

Study completion/discontinuation and primary reason for discontinuation will be summarized using the RS, separately for Part A and Part B. Each table will present the following, by treatment sequence:

- Number and percentage of participants that started the study
- Number and percentage of participants completing the study
- Number and percentage of participants discontinuing the study
- Number and percentage of participants discontinuing the study by primary reason for discontinuation.
- Part A only:
 - Number and percentage of participants that started substudy 1 and substudy 2
 - Number and percentage of participants completing substudy 1 and substudy 2
 - Number and percentage of participants discontinuing substudy 1 and substudy 2

Participants that started the study are defined as participants that were randomized. Participants completing the study are those participants completing the SFU visit AND who did not discontinue dosing or withdraw from the study for any reason before the SFU.

Participants that started substudy 1 and substudy 2 are defined as participants who started treatment period 1 and 4, respectively. Participants completing the substudy 1 and substudy 2 are those participants completing Washout period 3 and 6, respectively.

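### For participants who continue to Day 19, AEs that start in the esomeprazole lead-in (Days 14–18) are tabulated under the UCB0599 formulation given on Day 11

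*SAP*

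**What the plan says.** **Timing of esomeprazole.** Protocol Section 1.2 places it in the second substudy: "The PPI esomeprazole 40mg QD will be administrated on 20-consecutive days during substudy 2". Protocol Table 1-3, footnote a, says "In Treatment Period 4, an oral dose of 40mg esomeprazole will be administered QD for 20-consecutive days from Day 14 to Day 33", and then "On Day 19, Day 24, and Day 29, a single oral dose of 180mg UCB0599 will be administered 1 hour after intake of esomeprazole". The notes to SAP Table 1-3 give the same days, starting in the washout that follows Period 3.

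**Period boundaries.** SAP Table 5-1 gives Washout Period 3 as Days 12–18 and Treatment Period 4 as Day 19. SAP Table 5-8 starts the Period 3 AE window at the Period 3 dose (Day 11) and ends it "Prior to administration of treatment in Treatment Period 4". Each AE takes the treatment of the period it falls in. There is no esomeprazole category.

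**AE tables.** SAP Section 5.5.2 and Table 5-5 summarise Part A AEs by formulation only. An AE is treatment-emergent (TEAE) from the first treatment to 4 days after the last; later onsets are listed but not tabulated.

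**Objective and disposition.** The Part A secondary objective (Protocol Section 1.1, Overall design) is to "evaluate the safety and tolerability of a single dose UCB0599 alone under normal and elevated gastric pH". SAP Section 5.2 states: "Participants completing the substudy 1 and substudy 2 are those participants completing Washout period 3 and 6, respectively".

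**The concern.** The last five days of the Period 3 window are days on a second drug. They also follow a UCB0599 dose whose own sampling ends on Day 15. An AE starting on Day 16 in someone who goes on to the Day 19 dose is reported as a TEAE of whichever formulation that person took on Day 11, even if esomeprazole caused it. The protocol treats Day 14 as a boundary: it ties esomeprazole to the second substudy and schedules a physical examination and safety laboratory tests on that day. The AE rules do not.

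At stake are the absolute AE incidences by formulation, which serve the secondary objective. A related problem is that the same AE may be handled differently according to what the participant does next. If last treatment in the TEAE definition means UCB0599, an AE on Days 16–18 is a formulation TEAE when the participant continues. It is only listed when the participant stops after Day 11. TEAEs leading to withdrawal are a Part A secondary endpoint, so an AE in those days that causes withdrawal would drop out of the table meant to show it.

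**Working it through.** **Inputs.** UCB0599 doses on Days 1, 6, 11, 19, 24 and 29 (Protocol Table 1-1); esomeprazole Days 14–33; AE windows from SAP Table 5-8; TEAE limit of 4 days after last treatment (SAP 5.5.2); up to 42 participants, 7 in each of six sequences (Protocol 6.3).

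**Plan's own figure.** Esomeprazole duration: 33 − 14 + 1 = 20 days, as stated.

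**Window length** = last day − dose day + 1. Period 6 has no end in Table 5-8; the TEAE limit closes it at 29 + 4 = Day 33.

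| Period | Days | Length | Days on esomeprazole |
|---|---|---|---|
| 1 | 1–5 | 5 | 0 |
| 2 | 6–10 | 5 | 0 |
| 3 | 11–18 | 8 | 5 |
| 4 | 19–23 | 5 | 5 |
| 5 | 24–28 | 5 | 5 |
| 6 | 29–33 | 5 | 5 |

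Lead-in days are 5 of the 8 in Period 3 (62.5%). The hour between the two doses on Day 19 also falls in Period 3.

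**Person-days per formulation column, no dropout.** Each formulation is third in 2 of 6 sequences, so 2 × 7 = 14 participants take it in each period.
- Total: 14 × (5 + 5 + 8 + 5 + 5 + 5) = 14 × 33 = 462.
- Lead-in, Days 14–18: 14 × 5 = 70; 70/462 = 15.2%.
- Beyond 4 days after the Day 11 dose, that is Days 16–18: 14 × 3 = 42; 42/462 = 9.1%.
- With 36 completers the first share is the same: 60/396 = 15.2%.

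The counts are identical for A, B and C, so the misattribution is balanced across formulations.

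**Event counts.** The documents give no AE rate. If one assumes 0.01–0.03 new AEs per participant-day from any cause, the 42 × 5 = 210 lead-in person-days would carry 2.1–6.3 events, or 0.7–2.1 per formulation. This only illustrates scale; not all of these would be due to esomeprazole.

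**Related day counts.** The last Period 3 sample, 96 hours after the Day 11 dose, falls on Day 15, yet completing substudy 1 requires completing a washout that runs to Day 18. Someone who leaves on Day 17 with full normal-pH sampling counts as not completing substudy 1. By the SAP's relative-day formula, Day 18 is 18 − 11 + 1 = +8; Table 5-1 ends Washout Period 3 at +7.

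**The case against.** **No pH contrast is tabulated.** A reader might infer that the SAP as written biases a comparison of AEs at normal and elevated gastric pH, and might put the contamination at 5 of 18 normal-pH days (28%). The documents do not support that. Part A AE tables are by formulation, each column pools both conditions, and no hypothesis is tested. The 28% belongs to a table nobody plans; 15% is the share in the planned columns. The distortion would arise only if AEs were split by gastric condition, as the SAP does for vital signs and ECG (5.5.3.2.1 and 5.5.3.3.1).

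**Treatment in Period 4 could mean the Day 14 dose.** Footnote a to Protocol Table 1-3 places the Day 14 start in Treatment Period 4, and Protocol Table 6-1 lists esomeprazole among the Part A treatments. SAP Table 5-1, with Period 4 on Day 19, points the other way. The footnote reading does not cure the problem either: lead-in AEs would then go to the Period 4 formulation, which has not yet been given.

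**Days 14–18 are not esomeprazole alone.** Sampling of the Day 11 dose and the 4-day TEAE limit both reach Day 15, and Protocol Section 8.5 expects UCB0599 to be detectable for about 5 days. Closing Period 3 at the first esomeprazole dose would leave it 3 days against 5 elsewhere and under-count AEs after that dose. This stands, and it shapes the fix.

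**Not every lead-in AE is charged to a formulation.** If last treatment means UCB0599, onsets after Day 15 in someone who stops after Day 11 are only listed. This also stands, and is why the point is limited to participants who continue.

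**Events remain traceable.** Listings give onset times and relationship, TEAEs are also tabulated by relationship, and causality assessment considers concomitant therapy. That helps a reader of the listings but does not correct the incidence tables. Substudy completion is a disposition count that does not determine membership of the PK set, and the +7 has no shown effect on any analysis; both are minor.

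**Conclusion.** The point holds for participants who continue to Day 19. Under SAP Tables 5-1 and 5-8, AEs starting in the esomeprazole lead-in become TEAEs of the Day 11 formulation. Lead-in time is 15% of the person-days in each formulation column, and 9% lies beyond the SAP's own 4-day limit. Comparisons among the three formulations and all PK analyses are unaffected. Absolute AE incidence for every formulation is inflated to the extent that AEs start in those days.

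The shares assume 7 participants per sequence, no dropout, and Period 4 starting on Day 19 as in SAP Table 5-1. The uneven handling of participants who stop after Day 11 depends on reading last treatment as UCB0599, which the SAP leaves open. A biased pH contrast in the planned tables is not shown, although the secondary objective concerns both conditions and a later split would inherit the problem. This is a specific SAP correction that should be made; it does not threaten the primary analysis.

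**What to change.** 1. Add an esomeprazole lead-in row to SAP Tables 5-1 and 5-8.
2. Keep AEs under the Period 3 formulation up to 4 days after the Day 11 dose (Day 15), which matches the other periods, and flag onsets on Days 14–15 as on esomeprazole.
3. Report AEs starting after that and before the Day 19 UCB0599 dose in a separate lead-in column. State their treatment-emergent status, including for participants who stop before Day 19, and keep the last UCB0599 formulation in the listing.
4. Reconcile footnote a of Protocol Table 1-3 (Day 14 start within Period 4) with SAP Table 5-1 (Period 4 on Day 19).
5. Minor: define completion of substudy 1 by the Period 3 96-hour sample (Day 15), and correct Washout Period 3 to relative Day +2 to +8.

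With 42 participants, each formulation column would then hold 14 × 30 = 420 person-days in six equal 5-day windows, and the lead-in column 42 × 3 = 126; 3 × 420 + 126 = 1,386 = 3 × 462, so no time is lost.

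The cost is SAP wording, one extra AE column and the reconciliation of one protocol footnote, with no new data. The downside is that a late UCB0599 reaction starting on Days 16–18 would appear in the lead-in column; keeping the last formulation in the listing lets a reader trace it.
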